
2 ANALYSIS POPULATIONS

The following populations for analyses are defined:

Table 2 - Populations for analyses

Participants Analysis Set	Description
Screened	All participants who signed the informed consent form (ICF).
Enrolled/Randomized	All participants from the screened population who have been allocated to a randomized intervention for each target lesion by interactive response technology (IRT) regardless of whether the intervention was received.
Safety	All randomized participants who receive any amount of study drug (SAR444727 or placebo) will be included in the Safety population. The Safety population will be based on the intervention actually received and will be used for the summaries of all safety assessments.
Pharmacokinetic	All participants who received any amount of active study drug (SAR444727) and have at least one pharmacokinetics (PK) sample taken will be included in the PK population. The PK population will be used for the summaries of all PK data.
Efficacy	
- For double blind periodAll randomized participants who did actually receive at least 80% of prescribed study drug in the Blinded Period (for both lesion) and with at least 1 post-study drug administration efficacy (TSS) measurement.- For open label periodAll randomized participants who did actually receive at least 80% of prescribed study drug in the Blinded Period (for both lesion) and at least 80% of prescribed study drug in the Open-Label Period and at least 1 post-study drug administration efficacy (TSS) measurement.Participants will be analyzed according to the intervention they actually received.
Biomarker	All randomized participants with no important deviations impacting Biomarker measurements, for whom the Biomarker data are considered sufficient and interpretable.

Note: “Screened” means a participant's, or their legally acceptable representative's, agreement to participate in a clinical study following completion of the informed consent process.

Participants exposed to study intervention before or without being randomized will not be considered randomized and will not be included in any analysis population. The safety experience of these participants will be reported separately.

3 STATISTICAL ANALYSES

3.1 GENERAL CONSIDERATIONS

In general, unless otherwise specified, continuous data will be summarized using the number of observations available, mean, Standard Deviation (SD), median, range (minimum and maximum). Categorical and ordinal data will be summarized using the count and percentage of participants, as appropriate.

The baseline value is defined as the last available value before the first dose of Investigational Medicinal Product (IMP). For participants randomized but not treated, the baseline value is defined as the last available value before randomization.

Unless otherwise specified, analyses will be performed by intervention group (and overall, for baseline and demographics characteristics).

Observation period

The observation period will be divided into 3 segments:

- The **pre-treatment period** is defined as the period up to first IMP administration.
- The **treatment-emergent (TE) period** is defined as the period from the first IMP administration to the end of study (EOS) visit (EOS day included).
- The **post-treatment period** is defined as the period from the end of the TE period (starting the day after date of EOS visit).

Double blind analysis period is defined as the period from the date of first IMP up to the Day 15 (administration of first open label IMP) Visit or date of IMP discontinuation which ever comes first.

3.2 PRIMARY ENDPOINT(S) ANALYSIS

The primary endpoints detailed in this section are safety and tolerability of SAR444727 in participants with mild to moderate AD. Details are given in [Section 3.6](#).

3.2.1 Definition of endpoint(s)

The primary endpoints are incidence and severity of the adverse events (AEs) defined in [Section 3.6.2](#), the standard clinical parameters (vital signs and electrocardiograms [ECGs]), the laboratory parameters defined in [Section 3.6.3.1](#) and the assessment of local cutaneous tolerability defined in [Section 3.6.3.2](#).

3.2.2 Main analytical approach

All the safety analyses will be performed based on the safety population defined in [Table 2](#).

The safety evaluation will be based upon the review of the individual values (clinically significant abnormalities), descriptive statistics (summary tables and figures). No statistical significance tests will be performed on safety data. No imputation will be performed.

Safety measures include AEs, Treatment-Emergent AEs (TEAEs), Serious AEs (SAEs), AEs leading to study intervention, treatment discontinuation (permanent or not), study discontinuation, and death. Overall AEs, TEAEs, and SAEs incidence tables will be presented by System Organ Class (SOC), high level group term (HLGT), high level term (HLT), and preferred term (PT for each study period and overall, showing the number (n) and percentage (%) of participants experiencing an AE. They will be described according to maximum intensity and relation to the study intervention.

Proportion of participants with at least 1 TEAE, treatment emergent SAE, TEAE leading to death, and TEAE leading to definitive treatment discontinuation will be tabulated by study period and overall.

For the changes in vital signs, ECGs and laboratory tests, the incidence of potentially clinically significant abnormalities (PCSAs) occurring during the TE period will be summarized overall and by baseline status.

For analysis local cutaneous tolerability see [Section 3.6.3.2](#).

3.2.3 Sensitivity analysis

Not applicable.

3.2.4 Supplementary analyses

Not applicable.

3.3 SECONDARY ENDPOINT(S) ANALYSIS

The secondary endpoints are the Plasma SAR444727 concentrations at specified timepoints defined in [Section 3.7.1.1](#).

3.4 TERTIARY/EXPLORATORY ENDPOINT(S) ANALYSIS

There are two type of exploratory endpoints. The first exploratory endpoint is biomarker to evaluate changes in blood samples, skin tape stripplings, and skin biopsies. Details are given in [Section 3.7.1.2](#).

The second exploratory endpoints are efficacy endpoints during double-blind period and Open-label period based on the efficacy population. For the double-blind period, treatment differences or ratios will be assessed for SAR444727 Gel, 5% versus placebo at Day 8 and Day 15, and data will be presented by treatment for the blinded period, for scores assessed per lesion, and overall otherwise. During the Open-Label Period, efficacy will be assessed mainly at Days 29 and 43,

overall. For TSS, data will be described over the full course of the study presented by treatment received during the double-blind Period.

More specifically, the following endpoints will be assessed:

During double-blind period

- Change from Baseline in lesional TSS for the 2 target lesions at Day 8 and Day 15
- Change from Baseline in daily lesional Peak Pruritus Numeric Rating Scale (PP-NRS) score for the 2 target lesions up to Day 15 and at Day 15
- Change from Baseline in lesional validated Investigator Global Assessment for AD (v-IGA-AD) score for the 2 target lesions at Days 8 and 15
- Lesional v-IGA-AD response (proportion of participants with a lesional v-IGA-AD score of 0 [clear] or 1 [almost clear] and ≥ 2 -grade improvement from Baseline) at Days 8 and 15

During Open-label period

- For lesional TSS
 - Change from Baseline in lesional TSS for the 2 target lesions at Days 29 and 43
 - Change from Day 15 in lesional TSS for the 2 target lesions at Days 29 and 43
- For PP-NRS
 - Change in daily global PP-NRS from Day 15 to Days 29 and 43
 - Change in weekly average of PP-NRS from Day 15 to Days 29 and 43
 - Proportion of participants achieving at least 3-point reduction from Day 15 in daily global PP-NRS at Days 29 and 43 in participants with PP-NRS ≥ 3 at Day 15
 - Proportion of participants achieving at least a 4-point reduction from Day 15 in daily global PP-NRS at Days 29 and 43 in participants with PP-NRS ≥ 4 at Day 15
- For Eczema Area and Skin Severity Index (EASI)
 - Percent change from Baseline in EASI at Days 29 and 43
 - Percent change from Day 15 in EASI at Days 29 and 43
 - Proportion of participants with at least a reduction $\geq 50\%$ in EASI (EASI-50), with at least a reduction $\geq 75\%$ in EASI (EASI-75), with at least a reduction $\geq 90\%$ in EASI (EASI-90), and with at least a reduction $\geq 100\%$ in EASI (EASI-100), from Baseline to Days 15, 29 and 43
 - Proportion of participants with EASI-50, EASI-75, EASI-90, and EASI-100 from Day 15 to Days 29 and 43
- For v-IGA-AD
 - Proportion of participants achieving vIGA-AD of 0 (clear) or 1 (almost clear) at Day 29

- Proportion of participants achieving a vIGA-AD of 0 (clear) or 1 (almost clear) at Day 43
- Proportion of participants achieving vIGA-AD of 0 (clear) or 1 (almost clear) and a reduction of ≥ 2 points from Day 15 to Day 29
- Proportion of participants achieving vIGA-AD of 0 (clear) or 1 (almost clear) and a reduction of ≥ 2 points from Day 15 to Day 43
- For Body Surface Area (BSA)
 - Change from Day 15 in percentage of treatable BSA at Days 29 and 43
- For Scoring Atopic Dermatitis (SCORAD)
 - Percent change from Day 15 in SCORAD index at Days 29 and 43
- For Patient Oriented Eczema Measure (POEM)
 - Change from Baseline in POEM at Days 15, 29, and 43
 - Change from Day 15 in POEM at Days 29 and 43
 - Proportions of participants with a reduction in POEM ≥ 4 from Baseline at Days 15, 29 and 43 in participants with POEM ≥ 4 at Baseline
 - Proportions of participants with a reduction in POEM ≥ 4 from Day 15 at Days 29 and 43 in participants with POEM ≥ 4 at Day 15
- For Dermatology Quality of Life Index (DLQI)
 - Change from Baseline in DLQI at Days 15, 29, and 43.
 - Change from Day 15 in DLQI at Days 15, 29, and 43
 - Proportions of participants with a reduction in DLQI ≥ 4 from Baseline at Days 15, 29 and 43 in participants with DLQI ≥ 4 at Baseline
 - Proportions of participants with a reduction in DLQI ≥ 4 from Day 15 at Days 29 and 43 in participants with DLQI ≥ 4 at Day 15

Analyses for binary endpoints

The binary endpoints will be descriptively summarized using number, percentage and 95% confidence interval (CI) of percentage at each time point.

The proportion of subjects meeting the binary endpoint during the Open label period and corresponding exact 95% and 80% CI (95% CI and 80% CI respectively calculate with Wilson score method) will be summarized.

For the intra-participant comparison of SAR444727 vs placebo during the double blind period, binary endpoints (only for lesional v-IGA-AD response) will be analyzed for Day 8 and Day 15 separately, using a logistic regression model with intervention (SAR444727, placebo) as fixed effects. Odds ratio and difference in proportions as well as the corresponding 95% CI will be provided.

Analyses for continuous endpoints

The descriptive statistics (mean, SD, SEM, median, Q1, Q3, and range) for all continuous endpoints collected will be provided by treatment and time point on raw data, absolute changes or percent changes from baseline using the baseline efficacy population. Boxplots will also be provided by treatment and time point. Absolute or percent change from baseline and ratio from Baseline (mean \pm SEM and/or median with interquartile range) will also be produced by treatment for the double blind period.

For the intra-participant comparison of SAR444727 vs placebo, a linear mixed model (using restricted maximum likelihood) with repeated measurements will be fitted to estimate the difference in mean change in lesional TSS from Baseline to Day 15; and from Baseline to Day 8.

In addition to the visit, treatment, and visit-by-treatment interaction terms, the model includes the participant-specific baseline lesional TSS score covariate. Repeated measurements for visit are taken within participant and an unstructured covariance matrix will be used to model the within-subject variance-covariance errors. Baseline lesional TSS will be defined as the mean TSS from the two treated lesions at Baseline.

Change from baseline TSS= Intercept + TSS_{base} + VISIT + TRT + VISIT*TRT + Error

Least square means will be calculated for change from Baseline to Day15 for both treatments and differences of means for SAR444727 versus placebo with two-sided 95% CI will be derived from the model framework.

The model may be simplified if there are convergence issues.

SAS Statement

```
proc mixed data= method=reml;
  class VISITNUM USUBJID TRT;
  model CHGSC=BASESC TRT VISITNUM TRT*VISITNUM/solution ddfm=kr ;
  repeated VISITNUM*TRT/type=UN subject=USUBJID;
  lsmeans VISITNUM*TRT /slice=VISITNUM cl;
  estimate "SAR versus Plbo D15" TRT -1 1 VISITNUM*TRT 0 0 -1 1 /cl;
  estimate "SAR versus Plbo D8" TRT -1 1 VISITNUM*TRT -1 1 0 0 /cl;
run;
```

Participants with missing data at Baseline will not be included in the analysis. Participants with one or more post-dose timepoints will be included. Mixed model for repeated measures (MMRM) to account for missing data is used for the primary analysis under the missing at random (MAR) framework. Parameters will be estimated using restricted maximum likelihood method with the Newton-Raphson algorithm. Denominator degrees of freedom will be estimated using Kenward-Roger adjustment. All efficacy data after discontinuation of treatment will not be considered.

The same analysis will be conducted for lesional v-IGA-AD score at Days 8 and 15 and lesional PP-NRS. For the other efficacy parameters, only descriptive analyses will be provided.

The weekly average PP-NRS scores will be defined as the average of daily non-missing scores within the week preceding the given visit and will be calculated if there is a minimal amount of 4 non-missing scores.

The POEM score is a 5-point scale: 0 (“No days”), 1 (“1-2 days”), 2 (“3-4 days”), 3 (“5-6 days”) and 4 (“Every day”). The POEM score is calculated by summing the values for the 7 items.

If two or more questions are left unanswered the questionnaire is not scored.

The DLQI is a 4-point scale: 0 (“Not relevant”/“Not at all”), 1 (“A little”), 2 (“A lot”), 3 (“Very much”). For Question 7, “Prevented work or studying” is scored at 3. The DLQI is calculated by summing the score of each question.

The EASI-50/75/95/100 response is defined as a participant achieved a decrease by at least 50%/ 75%/ 95%/100% of EASI from Day 15.

Change in lesional TSS, PP-NRS (daily global and weekly average), EASI, BSA, SCORAD, POEM, DLQI during the Open label period will be analyzed descriptively. Estimations with 95% and 80% CIs may be derived. Sub-score of EASI by localization will also be provided.

Supplemental analyses

Where appropriate, supplemental analyses may be presented excluding observations after administration of rescue medication. No imputation will be made.

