4.1 OVERALL DESIGN

This is a Ph2a study that consists of a double-blind, intra-patient placebo-controlled treatment period and an open-label uncontrolled treatment period with objective to evaluate the safety, tolerability, PK and preliminary efficacy of PRN473 in up to 40 patients with mild to moderate AD. All patients are required to apply an emollient (except urea-containing or medicated emollients that are regulated as medical device) daily from Day -7 to Day 1 (see Section 6.2). On Day 1 (Baseline) of the Blinded Period, 2 target lesions with a difference no greater than 1 point in TSS will be randomly assigned to treatment in an intra-patient 1:1 manner, one lesion to PRN473 Gel, 5%, and the other to matching placebo. PRN473 Gel, 5% and matching placebo are weighed and applied BID (morning and evening) at a quantity of approximately 2.5 mg/cm² to a 100 cm² area of each target lesion on Days 1- 14 (Blinded Period). The investigational products will be applied at the study site, at the patient's home, or at an external clinic, where available.

During the Blinded Period, if the target lesion is less than 100 cm², the application area should include surrounding nonlesional skin (note: two target lesion skin biopsy specimens on Days 1 and 15 are only on lesional skin); if the target lesion is larger than 100 cm², only 100 cm² of the lesion should be marked and treated. On Days 15-42 (Open-Label Period), patients are instructed to apply PRN473 Gel, 5% BID to all AD-affected areas in a thin layer (excluding the scalp, palms, soles and genitals) and should continue to treat the assigned areas throughout the Open Label Period.

Safety assessments include application site tolerability assessments (Appendix 4, Section 10.4.1), vital signs, ECGs, physical examination, safety labs, and AEs.

To evaluate the PK (plasma concentrations) and biomarker of PRN473, blood samples will be collected at study visits accordingly to the SoA (Section 1.3).

Efficacy assessments of:

- The lesional PP-NRS will be administered daily predose during the Blinded Period (Days 1-14) and at predose Day 15.
- The lesional validated IGA will be performed predose at Baseline (Day 1), and Days 8 and 15.
- The lesion TSS (Appendix 4, Section 10.4.3) will be performed predose at Baseline (Day 1), Days 8, 15, and 29, and at End of Study/Early Termination visit (Day 43).

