3.8 INTERIM ANALYSES

An interim analysis (IA) for internal decision making will be implemented when approximately 25 or more of the planned participants have completed the Blinded Period (Day 15). Available data of the Open Label Period may be included in the analysis as appropriate.

The outcome is meant for internal decision making and may lead to early termination of the study only in case of unfavorable signals, or continuation without any changes.

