3.8.1 General considerations for the interim analysis

The Sponsor team that will analyze the data will include: a Medical Monitor, a biostatistician, a programmer, and a safety designee (global safety officer, [GSO]). Only the biostatistician and the programmer will have the access to unblinded individual data at the time of the analysis, which will not be provided to other Sponsor team members reviewing the data. Results will be provided in a restricted way following a dissemination plan, issued before any treatment code release for the analysis established upfront before the unblinding. The blinding will be preserved notably toward the Investigator, other site staff involved in the conduct of the trial, and participants.

The results of this IA will be considered preliminary results as they will not be based on final data. Final analysis will be conducted after database lock for the clinical study report.

Analyses methods and conventions described in the other sections of this SAP will be applied for all analyses as applicable.

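### The within-patient comparison of lesional vIGA-AD response uses a logistic model that ignores the pairing of the two lesions, so its 95% CIs do not fit the design

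*SAP*

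**What the plan says.** Protocol 4.1 sets up a split-lesion design: "2 target lesions with a difference no greater than 1 point in TSS will be randomly assigned to treatment in an intra-patient 1:1 manner". Each patient therefore supplies one active and one placebo observation.

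SAP 3.4, under the analyses for binary endpoints, introduces the model with "For the intra-participant comparison of SAR444727 vs placebo during the double blind period". It restricts the model to lesional vIGA-AD response, handles Day 8 and Day 15 separately, and compares the treatments "using a logistic regression model with intervention (SAR444727, placebo) as fixed effects". The output is stated as "Odds ratio and difference in proportions as well as the corresponding 95% CI will be provided". Nothing elsewhere in the SAP adds a subject effect, a clustered variance or a conditional likelihood for this endpoint, or says how the interval for the difference is obtained.

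For continuous endpoints the same section gives SAS code for TSS containing "repeated VISITNUM*TRT/type=UN subject=USUBJID", and it applies that analysis to the lesional vIGA-AD score and lesional PP-NRS. Protocol 9.4.3.1 also models the covariance between treatments within patient for TSS.

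Protocol 9.4.3.2 plans only summaries of lesional IGA response. The logistic model is a SAP addition, and SAP 3.9 does not list it as a change.

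**The concern.** An ordinary logistic model with treatment as its only term computes its standard error as if all lesions were independent. Two lesions on one patient, matched to within 1 TSS point at entry, are unlikely to respond independently. The vIGA-AD score is thus analysed as paired and the response derived from it is not, with no reason given.

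At stake is precision. The split-lesion design removes between-patient variation, and this model puts it back into the interval. In a study that describes itself as signal seeking, an over-wide interval can hide a signal. SAP 3.8.1 says of the interim analysis, planned at about 25 or more participants, that "Analyses methods and conventions described in the other sections of this SAP will be applied for all analyses as applicable", so the problem may recur where data are thinnest.

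**Working it through.** **Inputs.** From the documents: up to 40 pairs (SAP 4), about 25 or more at the interim (SAP 3.8), 95% intervals (SAP 3.4). They give no sample-size calculation, response rate or correlation, so there is no plan figure to reproduce. Assumed: response rates p1 (active) and p0 (placebo), and phi, the within-patient correlation of response.

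**1. Variance of the difference.** Write v1 = p1(1-p1), v0 = p0(1-p0), cov = phi·√(v1·v0).

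- Unpaired (as the SAP model implies): (v1 + v0)/n
- Paired: (v1 + v0 - 2cov)/n

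With p1 = 0.30, p0 = 0.15, n = 40: v1 + v0 = 0.2100 + 0.1275 = 0.3375, so the unpaired half-width is 1.96·√(0.3375/40) = 18.0 points. √(v1·v0) = 0.1636. At phi 0.3, 2cov = 0.0982 and the paired half-width is 1.96·√(0.2393/40) = 15.2 points.

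| phi | Unpaired | Paired | Equivalent pairs, of 40 | Equivalent pairs, of 25 |
|---|---|---|---|---|
| 0 | 18.0 | 18.0 | 40 | 25 |
| 0.1 | 18.0 | 17.1 | 36 | 23 |
| 0.3 | 18.0 | 15.2 | 28 | 18 |
| 0.5 | 18.0 | 12.9 | 21 | 13 |

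Half-widths are in percentage points for 40 pairs. Equivalent pairs = n·(v1 + v0 - 2cov)/(v1 + v0).

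**2. Negative correlation.** At phi -0.1 the unpaired interval for the difference is about 5% too narrow.

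**3. Lower rates.** At 15% versus 5%, 40 pairs, phi 0.3, the half-widths are 13.0 unpaired and 11.1 paired. At 15% versus 2%, phi cannot exceed 0.34 and the unpaired standard error is at most 14% too large.

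**4. Exact behaviour.** All paired 2x2 tables were enumerated at 30% versus 15%. Entries are coverage / how often the interval excludes no difference. Odds-ratio coverage is conditional on the odds ratio being estimable (99.8% of the probability at 40 pairs, 98.3% at 25).

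| Pairs, phi | Logistic OR | GEE OR, corrected variance, t | Unpaired Wald difference | Tango difference |
|---|---|---|---|---|
| 40, 0 | 96.4% / 34% | 97.1% / 30% | 94.3% / 37% | 95.0% / 35% |
| 40, 0.28 | 98.6% / 32% | 96.7% / 42% | 97.3% / 35% | 94.6% / 44% |
| 40, 0.43 | 99.4% / 29% | 96.2% / 52% | 98.5% / 33% | 94.5% / 54% |
| 25, 0.28 | 98.9% / 16% | 97.5% / 21% | 97.1% / 24% | 96.0% / 29% |
| 25, 0.43 | 99.6% / 14% | 96.5% / 25% | 98.4% / 21% | 96.7% / 37% |

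Compare like with like: logistic with GEE, and unpaired with Tango.

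**5. Worked table.** 12/40 active and 6/40 placebo responders. OR = (12·34)/(28·6) = 2.43. Logistic SE(log OR) = √(1/12 + 1/28 + 1/6 + 1/34) = 0.561, giving 0.81 to 7.30 however the pairs fall. The difference is 15 points, unpaired CI -3.0 to 33.0.

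| Respond on both lesions | phi | Corrected GEE CI for OR | Tango CI for difference |
|---|---|---|---|
| 4 | 0.34 | 0.93 to 6.32 | -0.6 to 31.1 |
| 5 | 0.49 | 1.04 to 5.65 | 1.4 to 30.1 |

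The estimates are the same in both rows. Only the paired intervals respond to how the pairs fall.

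**The case against.** **Under-specified rather than wrong.** The text calls the comparison intra-participant and speaks of fixed effects, which is mixed-model language, and it gives no code for the binary model. A subject term may have been intended. But none is written, and a programmer following the sentence would fit independent lesions. If a subject term was meant, the SAP has to say so.

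**Low materiality.** The protocol tests no hypotheses (9.1), the main efficacy comparison is TSS at Day 15 (9.4.3.1), the lesional vIGA-AD score gets a paired model, and no decision rule uses this interval. All of this stands and limits the weight of the point.

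**The interim link is partly out of sight.** Protocol 9.5 refers to a dedicated interim analysis plan, and SAP 3.8.1 applies its methods only where applicable. That the same model will be used at the interim is likely, not certain.

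**Mixed comparisons overstate the gain.** Setting logistic beside Tango mixes scale and method with pairing. At 25 pairs and phi 0.28, more than half of the 16% to 29% step comes from changing the scale and interval type. Like for like, the odds ratio goes from 16% to 21% and the difference from 24% to 29%. The pairing gain remains real and grows with phi.

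**The remedy is imperfect at low rates.** At 15% versus 5% and phi 0.3, the odds ratio is estimable with probability 87% at 40 pairs and 72% at 25. Corrected GEE coverage falls to 93.9% at 25 pairs, and to 92.2% at 15% versus 2% with 40 pairs. This stands, and it is a reason to lead with the difference: Tango coverage in those settings is 94.5% to 96.6%.

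**Other methods are valid.** A random-intercept or conditional logistic model, or an exact McNemar analysis, would also respect the pairing. The essential requirement is that both intervals do.

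**Conclusion.** The concern holds. As written, the 95% CI for the odds ratio ignores the pairing. So does the CI for the difference if it is derived from the same model, and the SAP names no other method. With complete pairs the point estimates are right.

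The size depends on rates and a correlation that the documents do not give. At 30% versus 15%, the interval for the difference is about 1.2 times too wide at phi 0.3 and 1.4 times at phi 0.5. It is correct at phi 0 and slightly too narrow if phi is negative. Positive correlation is an assumption, though a likely one. On that assumption the error is conservative and costs precision, not false-positive control. This should be corrected before analysis; it does not threaten the study's main conclusions.

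**What to change.** Replace the logistic sentence in SAP 3.4 with wording such as:

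> Lesional v-IGA-AD response at Day 8 and at Day 15 will be compared within participant. The main summary is the difference in proportions with a paired score (Tango) 95% CI. The marginal odds ratio will be estimated by GEE logistic regression with subject=USUBJID and a small-sample-corrected robust variance, and reported as not estimable if either treatment has no responders.

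Add the paired 2x2 table: response on both lesions, active only, placebo only, neither. If a conditional odds ratio with an exact CI is also shown, label it as a different estimand. Record the model in SAP 3.9, since the protocol planned summaries only.

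The cost is one SAP passage, one table and a few lines of code, with no new data. The double-blind efficacy population already requires at least 80% of prescribed dosing on both lesions, so few pairs should be incomplete.

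The downside is that these intervals are approximate at 25 to 40 pairs and gain nothing if phi is 0. In that case, at 40 pairs, the average Tango half-width is 18.2 points against 17.7 unpaired, and corrected GEE excludes an odds ratio of 1 in 30% of trials against 34% for logistic.
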